5. PATIENT MANAGEMENT

A. Informed Consent

Once the patient is determined to be eligible for the trial and prior to randomization into one of the treatment arms, appropriate informed consent will be obtained from the patient (or the patient's guardian). The informed consent form must have prior approval of the Institutional Review Board of the local institution.

B. Enrollment and Randomization

Enrollment will be by entering data from the Eligibility form on the clinical center's computer. This form will document the patient's eligibility for the trial. At the completion of data entry, the randomization assignment will be made by the computer. Age-eligible patients who are screened for the trial but found to be otherwise ineligible and those who are eligible but refuse consent will be recorded on the Eligibility form in order to maintain a record of the population from which trial participants are drawn.

Some patients who appear eligible initially will be found to have positive antibody status (either lymphocytotoxic or platelet) when baseline blood samples are analyzed by the central laboratory. These patients will be maintained on their assigned treatment arm, to the degree possible, and trial data will be collected on them. They will not, however, be included in the primary analysis of the trial.

C. Blinding

All TRAP investigators, the patient, the patient's private physician, and staff clinicians and nurses treating the patient, will be blinded to the treatment arm assigned. This will be accomplished by blinding the platelet product by placing all trial products in a standard pooling bag for administration by the transfusion service. Details of labeling of the blood product will be left to local option, as long as the randomly assigned treatment of the product is not identified. The blood center will maintain records linking the patient's name to the TRAP identification number, randomization assignment, and preparation of the blood products, so that the blind can be broken, if necessary.

TRAP coordinators will not be blinded to the treatment arm assigned. They will be responsible for monitoring the blood center's preparation of the blood product.

D. Transfusion Therapy

A prophylactic platelet transfusion may be given for platelet counts of $\leq 20,000/\mu\text{l}$. However, a transfusion at a higher platelet count may be required if the patient has significant bleeding. (If the patient is having a surgical procedure, a prophylactic platelet transfusion may be given for platelet counts of up to $50,000/\mu\text{l}$.) The standard dose of pooled random donor platelets for the trial will be 6 units. For the trial a dose of 4.2×10^{11} apheresis platelets will be considered equivalent to 6 units of pooled random donor platelets. However, it is possible that the standard platelet dose of 6 units of pooled random donor or 4.2×10^{11} apheresis platelets will need to be increased at local option for clinical reasons.

A prophylactic transfusion of red blood cells may be given at a hematocrit of ≤ 25 . However, the patient's clinical condition may require a transfusion at a higher hematocrit count.

Patients should remain on their assigned treatment arm for all transfusions through 8 weeks from enrollment (even if a second course of chemotherapy is required during this period). The assigned transfusions should only be discontinued in the event of

1. Severe adverse reactions to the platelet transfusions
2. Granulocyte transfusion
3. Withdrawal of informed consent
4. Death

There should be no change in platelet transfusion therapy for patients who are antibody positive if the patient is not platelet refractory. Blood centers will attempt to provide the assigned transfusions if at all possible. If an assigned transfusion cannot be provided, the blood center should provide a transfusion product which is as close as possible to the assigned product. In particular, the product should be prepared as assigned (UV-irradiated or filtered) if possible. The patient should be returned to the assigned transfusions as soon as possible.

E. Clinical Platelet Refractoriness

A patient is platelet refractory if the platelet corrected count increment (CCI) is < 5000 , i.e., the difference between the pre- and post-transfusion platelet counts per 10^{11} platelets transfused per square meter of body surface area is < 5000 . (An example of calculation of the CCI: if 4×10^{11} platelets were administered to a patient with a BSA of 2 m^2 and the platelet count rose to 50,000 from a pre-count of 10,000, the $\text{CCI} = \frac{(50,000-10,000)2}{4} = 20,000$.)

The post-transfusion count should be obtained within 60 minutes after completion of the transfusion. The pre-transfusion platelet count may be the morning count unless the transfusion is a test transfusion (see below). For test transfusions, the pre-transfusion count must be taken within 60 minutes of the transfusion.

The patient must be refractory to two consecutive ABO-compatible transfusions in the assigned transfusion treatment arm before the test transfusions begin.

First test transfusion - fresh platelets. If the patient is platelet refractory (CCI < 5000) to two consecutive ABO-compatible transfusions in the assigned treatment arm, he/she should be transfused with fresh random platelets prepared according to the patient's original treatment assignment. The fresh platelets should be as fresh as possible but must be transfused within 48 hours of collection. ABO compatibility is not required; however if a fresh transfusion is not ABO-compatible and fails, another fresh transfusion which is ABO-compatible is required to evaluate refractoriness. Patients who are not refractory to the fresh transfusion should continue on the assigned transfusion treatment arm, preferably with fresh platelets. Patients who are refractory to the "fresh" ABO-compatible platelet transfusion in the assigned treatment arm will be tested with an HLA-selected transfusion.

Second test transfusion - HLA-selected single donor platelets. Patients who are refractory (CCI < 5000) to the first test transfusion in the sequence should be transfused with the best available fresh HLA-selected single donor platelets, prepared as in the patient's originally assigned treatment arm. A "best" HLA matched transfusion is defined to be fully matched (an A match) or to have at most two blanks in the donor's HLA type with no incompatible antigens (B1U, B2U). ABO compatibility is not required; however if an HLA-selected transfusion is not ABO-compatible and fails, another HLA-selected transfusion which is ABO-compatible is required to evaluate refractoriness. The closest possible match should be used until a "best" match can be found. If an HLA-selected transfusion is successful, the patient is defined to be clinically alloimmune platelet refractory. The patient is defined to be clinically platelet refractory only if a "best" HLA-matched transfusion is not successful.

In both cases, further platelet transfusions should be prepared as the patient's originally assigned treatment arm prescribes; platelets may be HLA-selected, as available.

6. ENDPOINTS

A. Primary Endpoint

The primary outcome measure is the time to first alloimmune refractory episode within the first 8 weeks after the first transfusion, either platelet or red blood cell, in the trial. For the primary endpoint a patient must be both clinically platelet refractory and antibody positive (lymphocytotoxic, platelet reactive, or platelet specific).

Clinically platelet refractory is defined as either one of the following:

Clinically platelet refractory is defined as refractory (the corrected count increment, i.e., the difference between the pre- and post-transfusion platelet counts per 10^{11} platelets transfused per square meter of body surface area, is < 5000) to (1) a fresh platelet transfusion prepared by the assigned treatment and (2) a "best" HLA-matched transfusion prepared by the assigned treatment.

Clinically alloimmune platelet refractory is defined as (1) refractory (corrected count increment, i.e., the difference between the pre- and post-transfusion platelet counts per 10^{11} platelets transfused per square meter of body surface area, is < 5000) to a fresh platelet transfusion prepared by the assigned treatment and (2) responsive to an HLA-selected transfusion prepared by the assigned treatment.

Antibody positive is defined as any one of the following:

A positive lymphocytotoxic antibody is defined as at least one cell with greater than 60% kill, or two or more cells with greater than 40% kill, confirmed by repeat testing on the same sample.

A positive platelet antibody sample is defined as a reproducible antibody reaction with platelets as the test cell.

A positive platelet specific antibody sample is reproducibly platelet antibody reactive with a non-HLA platelet surface antigen.

B. Secondary Endpoints

The time to event (within 8 weeks) with regard to platelet refractoriness or alloantibody status alone will be secondary endpoints:

1. Clinical platelet refractoriness (platelet increment < 5000 per 10^{11} platelets transfused per square meter of body surface area) by 8 weeks.
2. Clinical alloimmune platelet refractoriness (platelet increment < 5000 per 10^{11} platelets transfused per square meter of body surface area)

by 8 weeks.

3. Lymphocytotoxic antibody status of the blood sample by 8 weeks. A positive antibody is defined as at least one cell with greater than 60% kill, or two or more cells with greater than 40% kill, confirmed by repeat testing.
4. Platelet reactive antibody status of the blood sample by 8 weeks. A positive reaction is defined as a reproducibly positive antibody reaction with platelets as the test cell.
5. Platelet specific antibody status of the blood sample by 8 weeks. A positive platelet specific antibody sample is reproducibly platelet antibody reactive with a non-HLA platelet surface antigen.

C. Other Outcome Measures

Other possible outcome measures include the following:

1. CMV status. Comparison will be made between CMV antibody negative patients who receive leukocyte-poor products versus those who receive standard products for CMV seroconversion. The last serum sample within 8 weeks will be compared to the baseline sample.
2. Leukemia status. Dates of response, relapse, death will be collected at each 6-month follow-up.
3. Antibody development and loss as determined from the weekly and monthly serum samples.
4. Type of antibody identified: lymphocytotoxic, platelet reactive, or platelet specific.
5. Bleeding events defined as follows:
 - a. Any central nervous system hemorrhage
 - b. Hematuria with clots
 - c. Bright red blood, melena, or tarry stools per rectum
 - d. Pulmonary hemorrhage (hemoptysis) followed by radiographic changes in the lungs
 - e. Retroperitoneal hemorrhage
6. Number of red blood cell and platelet transfusions required during and after the initial 8-week period.
7. Severe adverse reactions to a transfusion. Severe reactions are characterized by the following reactions during or within one hour after transfusion:
 - a. Increase in temperature greater than 3 degrees Fahrenheit (2 degrees centigrade)
 - b. Chills with rigors

- c. Extensive urticarial eruption
- d. Moderate to severe pulmonary symptoms (dyspnea, bronchospasm, or cyanosis)
- e. Anaphylaxis

8. Death.

7. DATA COLLECTION

A. Baseline

The following data will be collected at baseline:

1. Information necessary to document eligibility and to stratify at randomization: age, prior history of hematopoietic disorder, leukemia classification, chemotherapy program, prior transfusion status, prior pregnancy status.
2. Baseline serum/plasma sample.
3. Baseline patient data.

B. Acute Treatment Phase

During the first 8 weeks after the first transfusion (either platelet or red blood cell) in the trial the following data will be collected:

1. Weekly serum/plasma samples (even for patients who become platelet refractory or who suffer adverse reactions).
2. Data on response to each platelet transfusion, including adverse reaction data.
3. Data on each red blood cell transfusion.
4. Summary data on the 8-week outcome.
5. Serum sample at death.

In the event of a granulocyte transfusion or a bone marrow transplant during this period, no further data and no further serum samples will be collected.

C. Follow-up

Follow-up will continue for each patient until the completion of data collection. The following data will be collected during follow-up.

1. Monthly serum samples to 1 year.
2. Transfusion history of platelet transfusions to 1 year.
3. Transfusion history of red blood cell transfusions to 1 year.
4. Leukemic status at 6-month intervals for the total duration of the

trial. For patients entered during the first year of the trial this will be approximately three additional years (after the first year) of follow-up of disease status.

5. Mortality and other event (bone marrow transplant, etc.) data for the duration of the trial.

In the event of a granulocyte transfusion or a bone marrow transplant during the first year, no further data and no further serum samples will be collected.

8. PATIENT SAFETY AND CONFIDENTIALITY

A. Introduction

Patient safety is of primary concern in the trial, and confidentiality of all patient information is assured by all participating centers.

B. Risks of Procedures

During the course of venipunctures used for blood sampling, blood may escape from the vein into the surrounding tissues, possibly producing a bruise associated with swelling and tenderness. In addition, if sterility has not been maintained during the venipuncture, there may be a risk of developing an infection at the venipuncture site.

As with the transfusion of any blood product, a virus may be transmitted. All donor blood is routinely screened for the presence of hepatitis B, hepatitis C, ALT, core antibody to hepatitis B, the AIDS virus, the HTLV-1 virus, and, on occasion, for CMV. In spite of testing, infections with these or other viruses may rarely still result from the transfusion. In addition, because platelets are stored at room temperature, bacterial contamination may occur if there has been a break in the sterility of the system.

Acute adverse reactions to the transfusions are discussed below.

C. Adverse Reactions and Removal from Assigned Arm

The decision to discontinue the assigned transfusions for a patient who has an adverse reaction will rest with the principal investigator, in consultation with the attending physician. It is suggested that the assigned transfusions should be discontinued if the patient experiences the new onset of three or more episodes of moderate to severe transfusion reactions. These are characterized by the following reactions during or within one hour after transfusion:

1. Increase in temperature greater than 3 degrees Fahrenheit (2 degrees centigrade).
2. Chills with rigors.
3. Extensive urticarial eruption.
4. Moderate to severe pulmonary symptoms (dyspnea, bronchospasm, or cyanosis). Only two episodes of bronchospasm are required.

Anaphylactic reactions are not expected. If one should occur, the reaction should be carefully and promptly evaluated, and discontinuation of the

assigned transfusions should be considered.

The Coordinating Center will periodically present to the Data and Safety Monitoring Board reports on possible adverse reactions to blood products. These reports include the kind and frequency of adverse reactions, numbers of patients withdrawn from the assigned treatment arm, the reasons for these withdrawals, and medications given to prevent reactions.

D. Breaking the Blind

Situations may arise when it is in the best interest of the patient to identify the assigned blood product treatment. Such instances should be rare, as most problems can be managed without knowing the assigned treatment. In the event that the blind must be broken, either the principal investigator, the clinical coordinator, or the local blood center can be contacted. The coordinator will have recorded the assigned treatment on the patient's Eligibility form, which will be kept in the patient's TRAP file, and the blood center will also have a record of the assigned blood product treatment.

E. Confidentiality

It must be stressed to all clinical personnel that confidentiality of patient information must be preserved. No unauthorized personnel should have access to patient records or results of interviews or tests. All record storage should be appropriately secured, in locked rooms and/or locked cabinets.

No data containing patient identifiers will be maintained in the Coordinating Center database. Individual patients will be identified in the database only by a code number.

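### Section 8.D names the blinded principal investigator as a code-break contact and files the assignment on the Eligibility form, with no stated barrier, which does not fit the blinding in 5.C

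*Protocol*

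**What the plan says.** Section 5.C (Blinding) states: "All TRAP investigators, the patient, the patient's private physician, and staff clinicians and nurses treating the patient, will be blinded to the treatment arm assigned". It makes no exception for the principal investigator. The next paragraph names the one unblinded role at the clinical center: "TRAP coordinators will not be blinded to the treatment arm assigned". The reason given is that coordinators oversee how the blood center prepares the product. For emergencies 5.C relies on the blood center: "The blood center will maintain records linking the patient's name to the TRAP identification number, randomization assignment, and preparation of the blood products". The blind itself is protected by a common pooling bag and by labels that do not reveal how the product was treated.

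Section 8.D (Breaking the Blind) says that, when the blind has to be broken, "either the principal investigator, the clinical coordinator, or the local blood center can be contacted". It then names where the assignment is found. One source is the blood center's record. The other is the trial file: "The coordinator will have recorded the assigned treatment on the patient's Eligibility form, which will be kept in the patient's TRAP file".

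Section 8.C says: "The decision to discontinue the assigned transfusions for a patient who has an adverse reaction will rest with the principal investigator". The attending physician is consulted. The threshold, which counts reactions graded at least moderate, is advisory: "It is suggested that the assigned transfusions should be discontinued if the patient experiences the new onset of three or more episodes".

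Section 10.B treats patients taken off their assigned treatment as censored in the primary time-to-event analysis. It lists severe adverse reaction among the censoring mechanisms assumed independent of alloimmunization.

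**The concern.** A blinded person does not ordinarily serve as a code-break contact, because answering such a request means looking up the arm or being told it. Section 8.D gives the principal investigator that role on the same footing as the two parties who do hold the assignment. It also places the assignment on a form completed for eligibility purposes and kept in the patient's trial file, and says nothing about who may open that file.

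The principal investigator's judgment feeds the primary analysis in one place: removal from the assigned product after reactions. If that decision were made with knowledge of the arm, removal, and hence censoring, could differ between arms for reasons unrelated to the patient. The grading of transfusion reactions in section 6.C, such as how extensive an urticarial eruption is or how severe the pulmonary symptoms are, also involves judgment and would be open to the same influence.

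**Working it through.** The protocol gives no figure on this point and no arithmetic applies. The check is a side-by-side reading.

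1. **Who must be blind.** 5.C: all trial investigators. The principal investigator is one, and no other section makes an exception.

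2. **Who holds the assignment.** 5.C: the coordinators and the blood center. 8.D names the same two sources, the coordinator's entry on the form and the blood center's record. On who holds the code, the two sections agree.

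3. **Who can be asked to break the blind.** 5.C mentions only the blood center's records. 8.D lists three contacts, and the principal investigator is the only one of them who is blinded under 5.C. 8.D does not say whether that investigator passes on the request, authorizes it or obtains the answer. The sections part here.

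4. **Where the assignment is written.** Under 5.B, data from the Eligibility form are entered on the center's computer, which returns the assignment. Under 8.D, the coordinator records it on that form. The filing instruction is general, so it covers the form of each enrolled patient.

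5. **What keeps blinded investigators from the form.** 8.E asks for locked storage and excludes unauthorized personnel, but as a confidentiality rule. It does not say whether a blinded investigator is authorized to see the trial file. No other section deals with it.

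6. **What the person in step 3 decides.** 8.C gives the principal investigator the removal decision, under a threshold that is only suggested.

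7. **What removal does.** 10.A lists severe adverse transfusion reactions among the causes of withdrawal, and 10.B censors patients whose assigned treatment is discontinued. The argument 10.B gives for independence concerns death. For the other mechanisms it promises to compare times to censoring between alloimmunized and non-alloimmunized patients, and to test how robust the arm comparisons are to departures from independence.

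Steps 1 and 3 need reconciling. Steps 4 and 5 leave a gap. Steps 6 and 7 explain why the gap matters for this particular person.

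**The case against.** The strongest reply is that being a contact is not the same as knowing the arm. A principal investigator who authorizes a request, or refers the caller to the coordinator, stays blind, and 8.D names no source of the code beyond the two that 5.C allows. This stands: the text does not show that the principal investigator is unblinded. It does not show that the investigator only relays requests either, so the wording should settle the matter.

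The second reply is that the form is a coordinator's working document and that the Manual of Operations, which section 9.C says describes each form in detail, may restrict access. This is possible, and the manual is not at hand. A reader might infer that investigators routinely consult the Eligibility form and see the arm there. The protocol does not say that anyone but the coordinator uses the form after enrollment, nor that the trial file is the medical chart. What remains is that the protocol states where the assignment is kept without stating that it is shielded.

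The third reply is that the primary endpoint is well protected. Its components are a calculated count increment and central-laboratory antibody results, not investigator judgments. The monitoring board receives the numbers of and reasons for withdrawals from the assigned arm, the Coordinating Center reviews management decisions for adherence, and 10.B plans checks on censoring. All of this stands and limits the likely harm. It leaves open the discretionary removal decision, and those later checks cannot show whether a decision was made with knowledge of the arm.

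**Conclusion.** The point holds as an inconsistency between 5.C and 8.D with a modest possible consequence. The protocol requires a blind for all investigators, then lists one of them as a code-break contact and files the assignment with no stated barrier. That leaves a route to the arm for the person who decides on removal for adverse reactions.

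A reader might go further and conclude that the blind is lost at every center, or that censoring is biased. The document supports neither. Where a record is kept is not evidence that anyone read it. Bias would require the investigator to learn the arm, to be influenced by it, and to remove patients differently between arms. The protocol gives no rate for any of these steps, so a count of affected patients, or an effect on the hazard ratio, error rate or power, would be guesswork.

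The conclusion assumes that no document outside the protocol already restricts the form or defines the principal investigator's role in a code break. If one does, the protocol need only say so. The change is worth making because it costs little and protects a blind that the protocol itself sets.

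**What to change.** Reconcile 8.D with 5.C in three steps.

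- In 8.D, name only the unblinded coordinator and the blood center as code-break contacts. A request that reaches the principal investigator is referred to one of them.
- For future enrollees, record the assignment in a restricted coordinator or blood-center record, or under seal, instead of on the Eligibility form.
- Log each unblinding with its date, its reason and who learned the arm, so that the analysis can identify these patients.

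Make no change to the rule in 8.C for discontinuing assigned transfusions.

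The cost is a short wording change and a new place for one item. Enrollment had begun by this version (section 10.A gives January 14, 1991), so forms already completed may have to be masked or re-filed. The two parties who hold the code keep it. Because one contact is dropped, centers should confirm that the coordinator or the blood center can always be reached.
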